### **5.10.1. Permitted Medications**

Paracetamol or Acetaminophen, at doses of ≤ 2 grams/day is permitted for use from 48 h prior to the first dose of GSK1278863 and until completion of follow-up procedures.

Use of low dose (≤325mg/day) aspirin/acetylsalicylic acid is permitted for the duration of the study (from Screening to the follow-up visit at the end of the study).

Concomitant medications other than specified in Section 5.10 may be considered on a case by case basis by the Investigator in consultation with the GSK Medical Monitor.

Subjects receiving HRT and other drugs not specifically prohibited (see Section 5.10.2) are permitted to continue while on study.

#### **5.10.1.1. Inhibitors of BCRP**

Medications that are inhibitors of BCRP will be permitted in the study. These medications include omeprazole, lansoprazole, rabeprazole, and pantoprazole.

#### **5.10.1.2. Non-Drug Therapies**

Calcium, Vitamin D, and other vitamins and minerals may be permitted at the discretion of the Investigator or his/her designee. Refer to Study Procedural Manual (SPM) for an extended list.

### **5.10.2. Prohibited Medications and Non-Drug Therapies**

#### **5.10.2.1. Supplements**

Subjects must abstain from taking supplements (with the exception of vitamin or minerals), within 7 days (or 14 days if the drug is a potential enzyme inducer) or 5 half-lives (whichever is longer) prior to the first dose of GSK1278863 until completion of the

follow-up visit, unless in the opinion of the Investigator and sponsor it will not interfere with the study.

#### **5.10.2.2. NSAIDs**

Chronic use of NSAIDs will **not** be permitted with the exception of low dose ( $\leq 325$ mg/day) aspirin/acetylsalicylic acid for the duration of the study (from Screening to the follow-up visit at the end of the study).

#### **5.10.2.3. Immunosuppressants**

Immunosuppressant drugs and drugs used to treat malignancies (including corticosteroids at doses  $>10$  mg prednisolone per day or equivalent) within 2 weeks of first dose of GSK1278863 are specifically prohibited from Screening through the follow-up visit.

**Note:** Failed transplant subjects who are on peritoneal dialysis are eligible for participation in this study but should not be on immunosuppressive medications within 3 months prior to Screening.

#### **5.10.2.4. Inhibitors and inducers of CYP2C8**

The primary route of metabolism of GSK1278863 involves CYP2C8.

Strong inhibitors and inducers of CYP2C8 are prohibited from 14 days prior to the first dose of GSK1278863 until 7 days after the last dose of GSK1278863. These medications include gemfibrozil, rifampin/rifampicin, phenytoin, hyperforin supplements (e.g., St John's Wort), Phenobarbital/phenobarbitone.

## **6. STUDY ASSESSMENTS AND PROCEDURES**

This section lists the procedures and parameters of each planned study assessment. The exact timing of each assessment is listed in the Time and Events Table Section [6.1](#).

Whenever vital signs, 12-lead ECGs and blood draws are scheduled for the same nominal time, the assessments should occur in the following order:

- 12-lead ECG
- vital signs
- blood draws

The timing of the assessments is required to allow the blood draw to occur as close as possible to the nominal time.

Protocol waivers or exemptions are **not allowed** with the exception of immediate safety concerns. Therefore, adherence to the study design requirements, including those

specified in the Time and Events Table (Section 6.1), are essential and required for study conduct.

The timing and number of planned study assessments and procedures may be altered during the course of the study based on newly available data (e.g., to obtain data closer to the time of peak plasma concentrations) to ensure appropriate monitoring.

The change in timing or addition of time points for any planned study assessments must be approved and documented in a Note to File which is approved by the relevant GSK study team member and then archived in the study sponsor and site study files. This will not constitute a protocol amendment.

The IRB/IEC will be informed of any safety issues that require alteration of the safety monitoring scheme or amendment of the Informed Consent Form (ICF).

Additional safety tests (such as vital signs, physical exams, and clinical laboratory tests) may also be obtained during the course of the study based on newly available data, to ensure appropriate safety monitoring.

**No more than** 500 mL of blood will be collected over the duration of the study, including any extra assessments that may be required.

Refer to [Appendix 3](#) for details regarding PK sample time windows that will not be regarded as protocol deviations.

During the Follow-up Period, deviations of up to +2 days for clinical research unit visits will not be regarded as Protocol Deviations.

The actual date and time will be recorded for all procedures and the Investigator will make every effort to perform procedures at the scheduled nominal dates and times.

### 6.1. Time and Events Table

Informed consent for optional PGx (pharmacogenetics) research must be obtained before collecting a sample.

Protocol Activity	Screening (refer to Section 3.1)	Treatment														Follow Up (refer to Section 3.1)
	~Day -30	Day -1	Day 1	Day 2	Day 3	Day 4-6	Day 7	Day 8-10	Day 11	Day 12-13	Day 14	Day 15	Day 16	Day 17	Day 22	
Window															+2 days	
Informed Consent Process	X															
Demographics	X															
Medical/medication/drug/alcohol history	X															
Safety Assessments																
Concomitant Medications a		←=====X=====→														
Complete Physical	X															
Vital Signs	X	X												X	X	
12 - Lead ECG (refer to Section 6.3.3)	X	X												X		
Adverse Events Assessment/ SAE's a		←=====X=====→														
Brief Physical		X												X		
Laboratory Assessments																
Chemistry	X	X												X		
Hematology	X	X												X		
PGx Sampling		← collect one PGx sample after the start of dosing (preferably on Day 1) →														
Serum Pregnancy Test	X	X													X	

Protocol Activity	Screening (refer to Section 3.1)	Treatment														Follow Up (refer to Section 3.1)
	~Day -30	Day -1	Day 1	Day 2	Day 3	Day 4-6	Day 7	Day 8-10	Day 11	Day 12-13	Day 14	Day 15	Day 16	Day 17	Day 22	
Window															+2 days	
Hepatitis B Surface Antigen (HBsAg)	X															
Hepatitis C Antibody (HCVAb)	X															
Admission to Clinic (optional) b		X									X					
IP dosing (oral) c			X	X	X	X	X	X	X	X	X					
Discharge				X										X		
Blood PK samples			X d		X e		X e			X e	X d	X f	X g	X h		
Dialysate PK samples			X i								X i	X i				
Iron Binding Capacity (TIBC)	X															
Creatine Kinase (CPK) k				X		X		X		X		X				
ALT l				X		X		X		X		X				
Iron (Fe)	X															
Transferrin	X															
Ferritin	X															
Drug and Alcohol Screen m	X	X								X						
Estradiol (E2) (refer to Section 6.3.4)	X															
Follicle Stimulating Hormone (FSH) (refer to Section 6.3.4)	X															
Serum Vitamin B12 and folate	X															
EPO and Hepcidin			X d		X e		X e		X e		X d					
HIV Ab	X															
Hemoglobin (Hb) n				X		X		X								
Protein Binding											X d					

- a Both Adverse event monitoring and Concomitant Medication reviews will be conducted throughout the study starting from Day -1.
- b Subjects may remain in residence at the site from the afternoon of Day -1 through the last assessment on Day 17, at the discretion of the investigator or by request of the subject (refer to Section 3.1). Outpatients must return to the site for scheduled PK assessments.
- c Each dose will be administered within 30 min after completion of the night APD treatment or morning last fill of peritoneal dialysis fluid. Outpatients can self administer their daily dose
- d Sampling schedules within the day are given in Section 6.1.1.
- e Sample to be taken predose only.
- f Sample to be taken 24 h post Day 14 dose.
- g Sample to be taken 48 h post Day 14 dose.
- h Sample to be taken 72 h post Day 14 dose.
- i Aliquot of dialysate from the last drained dwell prior to dosing on Day 1. Aliquot for APD subjects may be collected from automated cycler drain/drain bag prior to dosing on Day 1.
- j In CAPD subjects, record volume and take aliquots of dialysate from each drain bag over 24 h dosing period starting at time of Day 14 dose. Aliquot for APD subjects is to be collected from APD collection drain bag over 24 h dosing period starting at time of Day 14 dose.
- k Measurement in addition to clinical chemistry assessment.
- l Measurement in addition to hematology assessment.
- m Test will be performed for drug and alcohol at Screening, Day-1, and Day 13 visits check-in for subjects who participate in the study as outpatient, and it must be negative prior to dosing.
- n Hemoglobin assessment will be by a HemoCue device.

**6.1.1. Study Procedures and Assessments for Plasma PK, EPO, Hepcidin & Protein Binding Sampling on Day 1 and Day 14**

Procedure	Time (in h relative to dosing)												
	Predose	0.5	1	2	3	4	6	8	12	16	24	48	72
DAY 1													
PK blood sample	X	X	X	X	X	X	X	X	X	X	X		
EPO and Hepcidin	X					X		X	X		X		
DAY 14													
PK blood sample	X	X	X	X	X	X	X	X	X	X	X	X	X
EPO and Hepcidin	X					X		X	X		X		
Protein Binding	X				X				X				

## 6.2. Demographic/Medical History Assessments

The following demographic parameters will be captured: date of birth (only year), gender, race and ethnicity.

Medical/medication/alcohol history will be assessed as related to the eligibility criteria listed in Section 4.2.

Baseline assessments are defined as the last pre-dose timepoint of each assessment (except ECG, which will be the average of the 3 ECGs obtained at that timepoint).

## 6.3. Safety

Planned timepoints for all safety assessments are listed in the Time and Events Table (Section 6.1).

Additional time points for safety tests such as vital signs, physical exams and laboratory safety tests may be added during the course of the study based on newly available data to ensure appropriate safety monitoring.

### 6.3.1. Physical Exams

- **A complete physical examination** will include assessments of the head, eyes, ears, nose, throat, skin, thyroid, neurological, lungs, cardiovascular, abdomen (liver and spleen), lymph nodes and extremities.

Height and weight will also be measured and recorded.

- **A brief physical examination** will include assessments of the skin, lungs, cardiovascular system, and abdomen (liver and spleen).

### 6.3.2. Vital Signs

- Vital sign measurements will be measured in supine position **after 5 min** rest and will include systolic and diastolic blood pressure, body temperature, and pulse rate.

### 6.3.3. Electrocardiogram (ECG)

- 12-lead ECGs will be obtained at each timepoint during the study using an ECG machine that automatically calculates the heart rate and measures PR, QRS, QT, and QTc intervals.

Subjects are required to rest quietly at supine position for **at least 10 min** before and during each ECG reading (subjects should remain comfortable).

Repeat measurements may be performed if there are any clinical abnormalities observed or if artifacts are present.

Below is the number of ECGs will be obtained at each timepoint:

- **Screening:** Three ECGs will be taken, at least 5 min apart. Take average of the three intervals to determine subject eligibility.
- **Day -1:** Three ECGs will be taken, at least 5 min apart. The average of the intervals from the three ECGs will determine the baseline (HR, PR, QRS, QTc).
- **Day 17:** A single ECG will be taken.

Refer to Section 5.3.2 for QTc withdrawal criteria and additional QTc readings that may be necessary.

### 6.3.4. Clinical Laboratory Assessments

Blood samples for Clinical Laboratory Assessments will be collected in the fasted state during the study at the time points indicated in the Time and Events Table (Section 6.1). Subjects are to be fasted for a minimum of 6 h prior to blood sample collections.

If screening results suggest that the blood sample was obtained without an appropriate fasting period, the clinical chemistry may be repeated once at the Investigator discretion.

The total volume of blood collected for planned Clinical Laboratory Assessments, pharmacodynamic and pharmacokinetic assessments from all subjects will **not exceed 500 mL** during the entire study period.

Hematology, clinical chemistry, and additional parameters to be tested are listed below.

Details for the preparation and shipment of samples will be provided by Quest.

Reference ranges for all safety parameters will be provided to the site by the laboratory.

If additional non-protocol specified laboratory assessments are performed at the site's local laboratory and result in a change in subject management or are considered clinically significant by the Investigator (for example SAE or AE or dose modification) the results must be captured and sent to GSK along with other study data as defined in [Appendix 4](#).

Hematology, clinical chemistry, and additional parameters to be tested are listed below:

#### Hematology

	RBC Indices:	Automated WBC Differential:
Platelet Count		
RBC Count	MCV	Neutrophils
WBC Count (absolute)	MCH	Lymphocytes
Reticulocyte Count	MCHC	Monocytes
Hemoglobin		Eosinophils
Hematocrit		Basophils

## Clinical Chemistry

BUN	Potassium	AST (SGOT)	Total and direct bilirubin
Creatinine	Chloride	ALT (SGPT)	Uric Acid
Glucose, fasting	Total CO 2	GGT	Albumin
Sodium	Calcium	Alkaline phosphatase	Total Protein
CPK			

**NOTE:** Details of Liver Chemistry Stopping Criteria and Follow-Up Procedures are given in Section 5.3.1.

### Other screening/lab tests

HIV	
Hepatitis B (HBsAg)	
Hepatitis C (Hep C antibody – if second generation Hepatitis C antibody positive, a hepatitis C RNA assay (or other third generation immunoassay) should be reflexively performed on the same sample to confirm the result)	
FSH and Estradiol (as needed in women of non-child bearing potential only)	
Alcohol and drug screen (to include at minimum: amphetamines, barbiturates, cocaine, opiates, cannabinoids and benzodiazepines).	
Erythropoietin	
TIBC	Serum iron
Serum Ferritin	Serum transferrin
Vitamin B-12	Folate

Out of range laboratory results may be repeated at the discretion of the Investigator.

When hemoglobin values achieve the threshold values defined in Section 5.3.3 (Safety Stopping Criteria), appropriate procedures (e.g., venesection or erythrocytapheresis) will be considered and implemented at the discretion of the Investigator until the values return below the thresholds.

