##### Efficacy

5. A subject is eligible to enroll and participate in this study if he/she has ESRD and is on peritoneal dialysis for at least 2 months with a combined weekly (urine and peritoneal dialysis output) Kt/V urea  $> 1.7$  measured at any time within last 3 months.
6. No history of peritoneal dialysis-associated peritonitis, peritoneal catheter tunnel (exit site) infection or leakage for at least 3 months before study.
7. Meets the following erythropoiesis stimulating agent (ESA) criteria:
  - Is ESA naïve (i.e., no ESA use within the previous 12 weeks of screening)
  - OR**
  - Agrees to discontinue ESA (if currently using ESA) for at least 7 days prior to first dose of GSK1278863 until completion of Follow-up visit.
    - a. If the subject has a scheduled ESA interval which is  $\leq 7$  days, ESA treatment must be discontinued for at least 7 days prior to first dose of GSK1278863
    - b. If the subject has a scheduled ESA interval which is  $> 7$  days, ESA treatment must be discontinued for at least the scheduled interval length (e.g., if ESA interval is 14 days, then ESA must be discontinued for  $\geq 14$  days) prior to the first dose of GSK1278863
8. Has a hemoglobin value:
  - For ESA naïve subjects:  $< 10.0$  g/dL

- For subjects receiving ongoing ESA treatment: stable Hgb 9.0-11.5 g/dL.

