  - Non-hypertensive subjects with normal baseline blood pressure that experience an increase in blood pressure to  $\geq$  160/100 mmHg that persists over 24 h. Any subject who demonstrates this increase in blood pressure will be followed to resolution, until any antihypertensive therapy is withdrawn.
  - Subjects with stable elevated blood pressure at baseline that further increases above baseline by either >20 mmHg systolic, >10 mmHg diastolic, or achieves  $\geq$  180/110 mmHg. To meet this criterion these elevations must persist longer than 24 h. Any subject who develops worsening hypertension requiring intervention will be followed to resolution, until any intervention therapy is withdrawn.
  - On Days 3, 7 and 11, subject's hemoglobin will be assessed prior to dosing using a HemoCue device. Should subjects have an absolute hemoglobin level > 11.0 g/dL, a second hemoglobin measurement will be obtained at the same study visit to confirm. If confirmed, permanently discontinue GSK1278863 and withdraw subject from the study.
  - On Days 3, 7 and 11, subject's hemoglobin will be assessed prior to dosing using a HemoCue device. Should subjects have an absolute hemoglobin level of <8.5 g/dL, a second hemoglobin measurement will be obtained at the same study visit. If confirmed, permanently discontinue GSK1278863 and withdraw subject from the study.
  - CPK level >5xULN without confirmed alternative etiology or if deemed clinically significant by the Investigator.

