7.6.1. Laboratory Values

Laboratory Parameter	Units	Clinical Concern Range	
		Low Flag	High Flag
Albumin	g/L	< 30 g/L	>55 g/L
Aspartate Aminotransferase	IU/L		≥3x ULRR
Alanine Aminotransferase	IU/L		≥3x ULRR
Bilirubin (total and direct/indirect)	μmol/L		≥2x ULRR
Calcium	mmol/L	> 0.5 mmol/L below LLRR	> 0.25 mmol/L above ULRR
Glucose, fasting	mmol/L	<3.9	>22
Sodium	mmol/L	<130	>150

Laboratory Parameter	Units	Clinical Concern Range	
		Low Flag	High Flag
Total CO2	mmol/L	<20	>32
GGT	IU/L		>=2ULRR
Alkaline phosphatase	IU/L		>=3xULRR
Uric Acid	Mg/dL		>6.0 mg/dL
Total Protein	IU/L	<LLRR	>15 g/L bove ULRR
Potassium (serum)	mmol/L	> 0.5 mmol/L below LLRR	> 1.0 mmol/L above ULRR

Laboratory Parameter	Units	Clinical Concern Range	
		Low Flag (< x)	High Flag (>x)
Hemoglobin	g/dL	< 7.5	>=13.0
Platelet Count	GI/L	< 80x GI/L	> 500x GI/L
WBC Count	GI/L	> 1x GI/L below LLRR	>5x GI/L above ULRR
Neutrophils	GI/L	< 0.5x LLRR	
Lymphocytes	GI/L	< 0.5x LLRR	

Laboratory Parameter	Units	Clinical Concern Range	
		Low Flag (< x)	High Flag (>x)
Ferritin	ng/mL		> 1200
TSAT	%	<15	>40

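### Protocol Section 6.3.4 sets its trigger for considering blood removal only by reference to Section 5.3.3, and the value this yields, above 11.0 g/dL, lies inside the entry range for ESA-treated subjects

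*Protocol*

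**What the plan says.** Four places bear on this point.

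- **Protocol 6.3.4, other screening/lab tests.** The trigger is given as follows: "When hemoglobin values achieve the threshold values defined in Section 5.3.3 (Safety Stopping Criteria), appropriate procedures (e.g., venesection or erythrocytapheresis) will be considered". No hemoglobin figure appears in the sentence. Its closing words name who decides and when the procedures end: "implemented at the discretion of the Investigator until the values return below the thresholds".
- **Protocol 5.3.3, upper threshold.** On Days 3, 7 and 11, before dosing and by HemoCue: "Should subjects have an absolute hemoglobin level > 11.0 g/dL, a second hemoglobin measurement will be obtained at the same study visit to confirm". Confirmation ends dosing permanently, and the subject is withdrawn.
- **Protocol 5.3.3, lower threshold.** Same days and device: "Should subjects have an absolute hemoglobin level of <8.5 g/dL, a second hemoglobin measurement will be obtained at the same study visit". The consequence is the same.
- **Protocol 4.2.1, inclusion criterion 8.** "For subjects receiving ongoing ESA treatment: stable Hgb 9.0-11.5 g/dL". ESA-naive subjects enter below 10.0 g/dL, with no lower limit stated.

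The SAP has its own hemoglobin limits for marking values of potential clinical importance (Section 7.6.1), with the low flag first and the high flag second: "Hemoglobin g/dL < 7.5 >=13.0".

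**The concern.** A sentence about an invasive procedure should let the investigator read off when it applies. This one does not. Its trigger is whatever Section 5.3.3 contains, and Section 5.3.3 contains one high and one low hemoglobin threshold. Once the reference is resolved, the trigger falls inside the range in which the protocol enrolls ESA-treated subjects as stable. For a subject who entered at, say, 11.2 g/dL, the provision can apply although nothing has changed, and its end condition asks for a hemoglobin below the level at which the subject was accepted. What is at stake is a safety provision that conflicts with the trial's own eligibility rule, in a population that Section 1.1.1 describes as anemic. Investigator discretion is the only safeguard, because the text supplies neither value nor direction.

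**Working it through.** There is no sample-size, power or alpha figure to reproduce. The check resolves the cross-reference and compares intervals, in g/dL.

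**1. Which threshold does 6.3.4 mean?**

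| Threshold in 5.3.3 | Does the opening clause of 6.3.4 reach it? | Does the end condition work? |
|---|---|---|
| > 11.0 | Yes | Yes: a high value comes down to below the threshold |
| < 8.5 | Yes, because the wording is plural and gives no direction | No: a value under 8.5 is already below both thresholds, so the end condition is met before anything starts |

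The whole sentence works only for > 11.0.

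**2. Does that trigger overlap with eligibility?**

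- ESA-treated entry range: 9.0 to 11.5, width 11.5 − 9.0 = 2.5.
- Part of it above the trigger: above 11.0 and up to 11.5, width 11.5 − 11.0 = 0.5.
- Share of the range width: 0.5 / 2.5 = 20%. This is not a share of subjects, because the documents give no distribution of entry hemoglobin.
- ESA-naive entry is below 10.0, so there is no overlap with > 11.0.

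An ESA-treated subject enrolled in the overlap and still there on Day 3 meets the upper threshold with no rise from entry.

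**3. Low side.** ESA-naive entry has no floor, so a subject below 8.5 can be eligible and meet the lower 5.3.3 threshold. The opening clause of 6.3.4 then applies literally, but step 1 shows that the sentence cannot operate there.

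**4. Timing and confirmation.** Section 5.3.3 ties its thresholds to three days and a second reading. Section 6.3.4 repeats neither condition and sits among the laboratory assessments, where hematology is scheduled at Screening, Day -1 and Day 17 (Section 6.1). Whether 6.3.4 carries over the 5.3.3 conditions is left open.

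**5. SAP flags against 5.3.3 stops.**

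- High side: stop at > 11.0, flag at ≥ 13.0. Values above 11.0 and below 13.0 meet a stop without a flag (13.0 − 11.0 = 2.0 wide).
- Low side: stop at < 8.5, flag at < 7.5. Values from 7.5 to below 8.5 meet a stop without a flag (8.5 − 7.5 = 1.0 wide).

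**The case against.** The strongest reply is that 6.3.4 mandates nothing. The two procedures are examples, they are to be considered, and the decision is the investigator's. That stands, and the point must not be read as a requirement to remove blood above 11.0 g/dL. It does not remove the conflict, because discretion is exercised against a trigger that the protocol leaves to be inferred.

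Four stronger readings are tempting, and the documents do not support them.

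- **That the protocol directs blood removal in subjects who are too low.** The opening clause could be read that way, but the end condition defeats it. What remains is a drafting ambiguity.
- **That the SAP contradicts the protocol on treatment, or regards 11 to 13 g/dL as unremarkable.** Section 7.6 of the SAP is a rule for marking values on listings. The SAP does not say that HemoCue readings are screened against it. Subjects stopped under 5.3.3 are withdrawn, and withdrawals with reasons are already tabulated and listed (SAP 8.1 and 14.1.5). The flag mismatch is real but minor.
- **That such procedures would distort the study's EPO and hepcidin data.** A confirmed value on Day 3, 7 or 11 leads to withdrawal, and EPO and hepcidin sampling ends 24 h after the Day 14 dose (Section 6.1.1). No effect on a primary endpoint is shown.
- **That an amendment left the cross-reference behind.** The amendment log records a higher upper stop (≥ 13.0 g/dL) before Amendment 1, and the part available lists no change to the 6.3.4 sentence. That would explain the mismatch but does not prove it, and the log shows no change to the lower threshold.

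It is also fair to say that ESA treatment stops at least 7 days before the first dose, so hemoglobin may have moved by Day 3. The overlap shows what can happen, not how often.

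**Conclusion.** The point holds for the upper threshold. Section 6.3.4 resolves to > 11.0 g/dL, and this conflicts with criterion 8 for ESA-treated subjects enrolled above 11.0 and up to 11.5 g/dL. The overlap is 0.5 g/dL, or 20% of the width of their entry range. The number of subjects affected cannot be derived from the documents. The plural reference that takes in < 8.5 g/dL is a secondary ambiguity. The unflagged bands in the SAP are a separate, minor matter.

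The conclusion rests on two readings: that the 5.3.3 thresholds meant in 6.3.4 are the two hemoglobin criteria now in that section, and that the end condition identifies the upper one. The documents give no numeric definition of anemia and none is assumed. Whether any procedure is suitable at any hemoglobin level is a clinical question on which no view is taken.

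**What to change.** - **Protocol.** Reconcile Section 6.3.4, Section 5.3.3 and inclusion criterion 8. Section 6.3.4 should state which 5.3.3 threshold and what value the sponsor's clinical team intends, and whether the 5.3.3 days and confirmatory reading apply. The choice is the sponsor's.
- **SAP, minor.** Check the hemoglobin row in Section 7.6.1 against the 5.3.3 thresholds and decide whether values that meet a stop should also be flagged.

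The cost is about one sentence in 6.3.4, any matching edit that the reconciliation calls for in 5.3.3 or criterion 8, and at most one row of the SAP table. No added subjects, visits or samples are needed.
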